11.7 Confidentiality of study documents and patient records

The investigator must ensure anonymity of the patients; patients must not be identified by names in any documents submitted to Novartis. Signed informed consent forms and patient enrollment log must be kept strictly confidential to enable patient identification at the site.

11.8 Audits and inspections

Source data/documents must be available to inspections by Novartis or designee or Health Authorities.

11.9 Financial disclosures

Financial disclosures should be provided by study personnel who are directly involved in the treatment or evaluation of patients at the site - prior to study start.

12 Protocol adherence

Investigators ascertain they will apply due diligence to avoid protocol deviations. Under no circumstances should the investigator contact Novartis or its agents, if any, monitoring the study to request approval of a protocol deviation, as no authorized deviations are permitted. If the investigator feels a protocol deviation would improve the conduct of the study this must

be considered a protocol amendment, and unless such an amendment is agreed upon by Novartis and approved by the IRB/IEC/REB it cannot be implemented. All significant protocol deviations will be recorded and reported in the CSR.

14.1 Appendix 1 - Diagnostic criteria for PMF, PPV MF, and PET-MF

Criteria for post-polycythemia vera myelofibrosis (Barosi 2008)
Required criteria: 1. Documentation of a previous diagnosis of polycythemia vera as defined by the WHO criteria (Tefferi2007b) 2. Bone marrow fibrosis grade 2–3 (on 0–3 scale) ³ or grade 3–4 (on 0–4 scale) ^{4,a}
Additional criteria (two are required): 1. Anemia ^b or sustained loss of requirement of either phlebotomy (in the absence of cytoreductive therapy) or cytoreductive treatment for erythrocytosis 2. A leukoerythroblastic peripheral blood picture 3. Increasing splenomegaly defined as either an increase in palpable splenomegaly of ≥ 5 cm (distance of the tip of the spleen from the left costal margin) or the appearance of a newly palpable splenomegaly 4. Development of ≥ 1 of three constitutional symptoms: $>10\%$ weight loss in 6 months, night sweats, unexplained fever ($>37.5^{\circ}\text{C}$)
^a Grade 2–3 according to the European classification: ³ diffuse, often coarse fiber network with no evidence of collagenization (negative trichrome stain) or diffuse, coarse fiber network with areas of collagenization (positive trichrome stain). Grade 3–4 according to the standard classification: ⁴ diffuse and dense increase in reticulin with extensive intersections, occasionally with only focal bundles of collagen and/or focal osteosclerosis or diffuse and dense increase in reticulin with extensive intersections with coarse bundles of collagen, often associated with significant osteosclerosis. ^b Below the reference range for appropriate age, sex and altitude considerations.

Criteria for post-essential thrombocythemia myelofibrosis (Barosi 2008)
Required criteria: 1. Documentation of a previous diagnosis of essential thrombocythemia as defined by the WHO criteria (Tefferi 2007b) 2. Bone marrow fibrosis grade 2–3 (on 0–3 scale) ³ or grade 3–4 (on 0–4 scale) ^{4,a}
Additional criteria (two are required): 1. Anemia ^b and a $\geq 2\text{mg ml}^{-1}$ decrease from baseline hemoglobin level 2. A leukoerythroblastic peripheral blood picture 3. Increasing splenomegaly defined as either an increase in palpable splenomegaly of ≥ 5 cm (distance of the tip of the spleen from the left costal margin) or the appearance of a newly palpable splenomegaly 4. Increased LDH (above reference level) 5. Development of ≥ 1 of three constitutional symptoms: $>10\%$ weight loss in 6 months, night sweats, unexplained fever ($> 37.5^{\circ}\text{C}$)
^a Grade 2–3 according to the European classification: ³ diffuse, often coarse fiber network with no evidence of collagenization (negative trichrome stain) or diffuse, coarse fiber network with areas of collagenization (positive trichrome stain). Grade 3–4 according to the standard classification: ⁴ diffuse and dense increase in reticulin with extensive intersections, occasionally with only focal bundles of collagen and/or focal osteosclerosis or diffuse and dense increase in reticulin with extensive intersections with coarse bundles of collagen, often associated with significant osteosclerosis. ^b Below the reference range for appropriate age, sex and altitude considerations.

Diagnostic criteria for primary myelofibrosis (Arber et al., 2016)

Criteria for the diagnosis of primary myelofibrosis (PMF)

Diagnosis of overt PMF requires meeting all three major criteria, and at least one minor criterion
Major Criteria

 1. Presence of megakaryocytic proliferation and atypia, accompanied by either reticulin and/or collagen fibrosis grades 2 or 3* 2. Not meeting WHO criteria for ET, PV, BCR-ABL1+ CML, myelodysplastic syndromes, or other myeloid neoplasms 3. Presence of JAK2, CALR or MPL mutation or in the absence of these mutations, presence of another clonal marker** or absence of reactive myelofibrosis***
Minor Criteria

Presence of at least one of the following, confirmed in two consecutive determinations:
 
 a. Anemia not attributed to a comorbid condition b. Leukocytosis >11 x 10⁹/L c. Palpable splenomegaly d. LDH increased to above upper normal limit of institutional reference range e. Leukoerythroblastos

* Grading of myelofibrosis: Semiquantitative grading of BM fibrosis (MF) with minor modifications concerning collagen and osteosclerosis (Fiber density should be assessed only in hematopoietic areas): MF-0 Scattered linear reticulin with no intersections (cross-overs) corresponding to normal BM MF-1 Loose network of reticulin with many intersections, especially in perivascular areas MF-2 Diffuse and dense increase in reticulin with extensive intersections, occasionally with focal bundles of thick fibers mostly consistent with collagen, and/or focal osteosclerosis (In grades MF-2 or MF-3 an additional trichrome stain is recommended) MF-3 Diffuse and dense increase in reticulin with extensive intersections and coarse bundles of thick fibers consistent with collagen, usually associated with osteosclerosis (In grades MF-2 or MF-3 an additional trichrome stain is recommended)
 
** in the absence of any of the 3 major clonal mutations, the search for the most frequent accompanying mutations (e.g. ASXL1, EZH2, TET2, IDH1/IDH2, SRSF2, SF3B1) are of help in determining the clonal nature of the disease
 
*** BM fibrosis secondary to infection, autoimmune disorder or other chronic inflammatory conditions, hairy cell leukemia or other lymphoid neoplasm, metastatic malignancy, or toxic (chronic) myelopathies

14.2 Appendix 2 - Eastern Cooperative Oncology Group performance status

Grade	Performance Status
0	Fully active, able to carry on all pre-disease performance without restriction
1	Restricted in physically strenuous activity but ambulatory and able to carry out work of a light or sedentary nature, e.g., light house work, office work
2	Ambulatory and capable of all self-care but unable to carry out any work activities. Up and about more than 50% of waking hours
3	Capable of only limited self-care, confined to bed or chair more than 50% of waking hours
4	Completely disabled. Cannot carry on any self-care. Totally confined to bed or chair
5	Dead

14.3 Appendix 3 - Bone marrow biopsy evaluation (Arber et al., 2016) (when performed, they are not mandatory)

[figure not shown]
Fibrosis density should be assessed in hematopoietic areas. Grading of myelofibrosis: Semi quantitative grading of BM fibrosis (MF) with minor modifications concerning collagen and osteosclerosis*

Fibrosis Grade	Description
MF-0	Scattered linear reticulin with no intersections (cross-overs) corresponding to normal BM
MF-1	Loose network of reticulin with many intersections, especially in perivascular areas
MF-2	Diffuse and dense increase in reticulin with extensive intersections, occasionally with focal bundles of thick fibers mostly consistent with collagen, and/or focal
MF-3	Diffuse and dense increase in reticulin with extensive intersections and coarse bundles of thick fibers consistent with collagen, usually associated with osteosclerosis**
* Fiber density should be assessed only in hematopoietic areas	
** In grades MF-2 or MF-3 an additional trichrome stain is recommended	

14.4 Appendix 4 - Patient reported outcomes – Questionnaires

MF-7 Myelofibrosis 7 Item Symptom Scale

Myelofibrosis 7 Item Symptom Scale (MF-7)	
Symptom	0 to 10 Ranking
Select the one number that describes the worst severity you have experienced with each of the following in the past 24 hours	
Tiredness	(Absent) 0 1 2 3 4 5 6 7 8 9 10 (Worst Imaginable)
Filling up quickly when you eat	(Absent) 0 1 2 3 4 5 6 7 8 9 10 (Worst Imaginable)
Abdominal discomfort	(Absent) 0 1 2 3 4 5 6 7 8 9 10 (Worst Imaginable)
Night Sweats	(Absent) 0 1 2 3 4 5 6 7 8 9 10 (Worst Imaginable)
Itching (pruritus)	(Absent) 0 1 2 3 4 5 6 7 8 9 10 (Worst Imaginable)
Bone pain (diffuse not joint pain or arthritis)	(Absent) 0 1 2 3 4 5 6 7 8 9 10 (Worst Imaginable)
Pain under ribs on left side	(Absent) 0 1 2 3 4 5 6 7 8 9 10 (Worst Imaginable)

14.5 Appendix 5 - List of CYP3A4 inhibitors and inducers

Table 14-1 List of CYP3A4 inhibitors and inducers

Category	Drug Names
Strong inhibitors ^a of CYP3A	boceprevir, clarithromycin, cobicistat, conivaptan, danoprevir/ritonavir, eltegravir/ritonavir, grapefruit juice ¹ , idelalisib, indinavir, itraconazole, ketoconazole, lopinavir/ritonavir, LCL161, mibefradil, nefazodone, nelfinavir, posaconazole, ritonavir, saquinavir, sequinavir/ritonavir, telaprevir, telithromycin, voriconazole, indinavir/ritonavir, tipranoavir/ritonavir, troleandomycin,
Moderate inhibitors ^b of CYP3A	amprenavir, aprepitant, atazanavir, atazanavir/ritonavir, casopitant, cimetidine, ciprofloxacin, crizotinib, cyclosporin, duranavir, darunavir/ritonavir, diltiazem, dronedarone, erythromycin, faldaprevir, fluconazole ² , fosamprenavir, grapefruit juice ¹ , imatinib, lomitapide, netupitant, nilotinib, schisandra sphenanthera ³ , tofisopam, verapamil
Strong inducers ^c of CYP3A	avasimibe, carbamazepine, enzalutamide, mitotane, phenytoin, rifampin, St. John's wort ³ , rifabutin, phenobarbital,
Moderate inducers ^d of CYP3A	bosentan, efavirenz, etravirine, genistein ³ , lersivirine, lopinavir, modafinil, nafcillin, ritonavir, semagacestat ⁴ , talviraline ⁴ , thioridazine, tipranavir, ,

The list of CYP inhibitors and inducers was compiled from the FDA's "Guidance for Industry, Drug Interaction Studies," from the Indiana University School of Medicine's "Clinically Relevant" Table (Flockhart 2007) and from the University of Washington's Drug Interaction Database. Note that this may not an exhaustive list. Please refer to footnotes.
 
 Effect seems to be due to CYP2C19 inhibition by ethinyl estradiol. Fluconazole is a dual CYP3A4 and CYP2C9 inhibitor. Fluconazole is a strong CYP2C9 inhibitor based on the AUC ratio of omeprazole, which is also metabolized by CYP3A; fluconazole is a moderate CYP3A inhibitor. Herbal product. Drugs not available in the US Market. 
^aA strong inhibitor for a specific CYP is defined as an inhibitor that increases the AUC of a sensitive substrate for that CYP by equal or more than 5-fold.
 
^bA moderate inhibitor for a specific CYP is defined as an inhibitor that increases the AUC of a sensitive substrate for that CYP by less than 5-fold but equal to or more than 2-fold
 
^cA strong inducer for a specific CYP is defined as an inducer that decreases the AUC of a sensitive substrate for that CYP by equal or more than 80%.
 
^dA moderate inducer for a specific CYP is defined as an inducer that decreases the AUC of a substrate for that CYP by 50-80%.
	

Dual CYP2C9 and CYP3A4 inhibitors:

Fluconazole: avoid the concomitant use of ruxolitinib with fluconazole doses ≥ 200 mg daily; If clinically necessary to use doses ≥ 200 mg daily consultation with Sponsor is required. Please refer to [Section 6.4.2](#); Permitted concomitant therapy requiring caution and/or action.

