6.4.2 Permitted concomitant therapy requiring caution and/or action

The following medications have restrictions on use, dose, or require changes to the way in which ruxolitinib is administered during the study:

- In patients for whom warfarin or heparin use will be initiated, the degree of thrombocytopenia should be considered, coagulation parameters monitored, and dose of anticoagulant adjusted accordingly. If anticoagulation is required during ruxolitinib administration, low molecular weight heparin is preferred, particularly in patients who are: elderly, history of CHF, diabetic, hepatic or renal disease, or atrial fibrillation (first episode).
- Low dose aspirin (≤ 150 mg/day) and non-steroidal anti-inflammatory agents (acetaminophen, ibuprofen) may be used. Aspirin doses > 150 mg are prohibited.
- Inducers or inhibitors of the metabolizing enzyme CYP3A4 (Appendix 5)
- When concomitant administration of a strong (potent) inhibitor of CYP3A4 metabolizing enzymes or dual CYP2C9/CYP3A4 inhibitors (Appendix 5) is required for patient management, the dose of ruxolitinib tablets must be reduced by approximately 50% to be administered twice daily by decreasing the twice daily dose or by decreasing the frequency of dosing to the corresponding once daily dose when twice daily dose is not practical.
 - Note: No dose adjustment of ruxolitinib is needed for use with topical ketoconazole.

- Note: More frequent monitoring of hematology parameters and clinical signs and symptoms of ruxolitinib related adverse reactions is recommended upon initiation of a strong (potent) CYP3A4 inhibitor.
- No dose adjustment will be made when moderate systemic CYP3A4 inducers ([Appendix 5](#)) are co-administered with study treatment.
- Granulocyte growth factors are not allowed while study treatment is being administered but may be used for severe neutropenia at the Investigator's discretion while study medication is being withheld.
- Certain herbal supplements see [Appendix 5](#) are prohibited. Because the composition, pharmacokinetics and metabolism of many herbal supplements are unknown, the concurrent use of all herbal supplements is strongly discouraged during the study however if used during the trial please ensure the treatment is entered on the proper eCRF page (see [Section 6.4.1](#)).

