7.1.4 Discontinuation of study treatment

Patients may voluntarily discontinue from the study treatment for any reason at any time. If a patient decides to discontinue from the study treatment, the investigator should make a reasonable effort (e.g. telephone, e-mail, letter) to understand the primary reason for this decision and record this information in the patient's chart and on the appropriate CRF pages. They may be considered withdrawn if they state an intention to withdraw, fail to return for visits, or become lost to follow-up for any other reason.

The investigator may discontinue study treatment for a given patient if, he/she believes that continuation would be detrimental to the patient's well-being.

In addition to mandatory dose interruptions and/or reductions of Study treatment listed in [Section 6.3](#), study treatment may also be discontinued under the following circumstances:

- Consent is withdrawn
- Further participation would be injurious to the patient's health or well-being in the investigator's medical judgment
- The study is terminated
- Disease progression
- Pregnancy
- Unacceptable toxicity
- The following deviations from the prescribed dose regimen for study treatment . If the study drug is interrupted for any reason for more than 8 weeks, dosing may not be restarted, except in the case of splenectomy, for which a maximum 12 week period of study drug interruption is permitted.
- Use of prohibited treatment refer to Appendix 5
- Any other protocol deviation that results in a significant risk to the patient's safety
- Discontinuation from the study for any other reason per the Investigator's judgement

Adverse events requiring discontinuation are listed in [Section 6.3.4](#).

Patients who discontinue study treatment should undergo an end of study treatment visit and then enter the follow-up epoch or period.

The investigator must also contact the IRT to register the patient's discontinuation from study treatment.

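### Table 14-1 puts stand-alone ritonavir and grapefruit juice in two CYP3A classes each, so Protocol Section 6.4.2 gives conflicting dose instructions for ritonavir and an unclear one for grapefruit juice

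*Protocol*

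**What the plan says.** Protocol Section 6.4.2 has two dose rules that cite Appendix 5.

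- When a strong CYP3A4 inhibitor or a dual CYP2C9/CYP3A4 inhibitor is needed to manage the patient, "the dose of ruxolitinib tablets must be reduced by approximately 50% to be administered twice daily", or the frequency is cut to the corresponding once-daily dose.
- For moderate inducers: "No dose adjustment will be made when moderate systemic CYP3A4 inducers" are given with study treatment.

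Table 14-1 in Appendix 5 supplies the classes. Grapefruit juice is among the strong inhibitors ("boceprevir, clarithromycin, cobicistat, conivaptan, danoprevir/ritonavir, eltegravir/ritonavir, grapefruit juice") and among the moderate inhibitors ("fosamprenavir, grapefruit juice"). Ritonavir, as a single entry, is among the strong inhibitors ("nelfinavir, posaconazole, ritonavir, saquinavir") and among the moderate inducers ("modafinil, nafcillin, ritonavir, semagacestat"). Grapefruit juice carries footnote mark 1 in both rows. Footnote 1 reads "Effect seems to be due to CYP2C19 inhibition by ethinyl estradiol".

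Exclusion criterion 7 (Section 5.3) also uses the strong-inhibitor class, at screening. Section 7.1.4 lists, among the circumstances in which treatment may be stopped, "Use of prohibited treatment refer to Appendix 5".

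**The concern.** Table 14-1 is an operative table: the class it assigns decides whether a mandatory dose reduction applies, and it bears on eligibility. A substance in two classes leaves the site to choose. The trial enrols only patients with hemoglobin below 10 g/dL, and the protocol describes anemia, thrombocytopenia and neutropenia as dose-related, so an unresolved dose instruction matters more here than in a less fragile population. It also weakens the protocol's standing as a common dosing rule across centers, since a monitor could not say which of two sites had deviated.

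The Section 7.1.4 pointer is a related, smaller matter: it refers the reader to Appendix 5 for prohibited treatment, but Appendix 5 is an interaction list.

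**Working it through.** The plan states no figure to reproduce. The check compares the four rows of Table 14-1 in pairs, by exact name with footnote marks removed, and then maps each duplicate to the dose rules.

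**Step 1. Overlaps between rows**

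- Strong inhibitors and moderate inhibitors: grapefruit juice.
- Strong inhibitors and moderate inducers: ritonavir.
- The other four pairs: none.

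**Step 2. Can both listings be true?**

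For the inhibitor classes, no. The notes to the table define a strong inhibitor as raising a sensitive substrate's AUC at least 5-fold, and a moderate one as raising it at least 2-fold but less than 5-fold. Footnote 1 does not mention grapefruit juice, so it does not settle the class. Footnotes 2 (fluconazole), 3 (herbal products) and 4 (drugs not marketed in the US) fit the entries they mark, so a general shift of the footnote numbering is unlikely.

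For ritonavir, a drug could in principle both inhibit and induce. The protocol shows how it treats a drug with two properties: fluconazole has an explanatory footnote, a paragraph of its own in Appendix 5 and a dual-inhibitor rule in Section 6.4.2. Ritonavir has none of these.

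**Step 3. Which dose rule applies?**

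- Ritonavir as strong inhibitor: Section 6.4.2, reduce by about 50%.
- Ritonavir as moderate inducer: Section 6.4.2, no adjustment.
- Grapefruit juice as strong inhibitor: Section 6.4.2, reduce by about 50%, if it is needed to manage the patient.
- Grapefruit juice as moderate inhibitor: Section 6.4.2 has no rule. A recommendation against adjustment for moderate inhibitors appears only in the product characteristics in Appendix 6 (label section 4.5).

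For ritonavir the two instructions imply doses in the ratio 1 / 0.5 = 2.

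**Step 4. Does it reach the analysis?**

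The success criteria, the 50-patient sample size and the handling of missing spleen length do not refer to CYP3A class. The SAP's per-protocol exclusions (SAP Section 2.2.3) include potent CYP3A4 inducers, but neither duplicated substance is in the strong-inducer row. They do not include exclusion criterion 7.

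**Step 5. The Section 7.1.4 pointer**

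Appendix 5 omits agents that Section 6.4.3 prohibits, among them hydroxyurea, interferon, thalidomide, busulfan, lenalidomide, anagrelide and other JAK inhibitors. It includes strong inhibitors and moderate inducers that Section 6.4.2 permits with conditions. It is still the list that Section 6.4.3 cites for prohibited potent inducers and Section 6.4.2 cites for prohibited herbal supplements. The pointer is therefore incomplete, but it has a use.

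**The case against.** The strongest reply is that almost nobody will be affected. Known HIV infection, infection requiring therapy, active hepatitis B or C, and strong CYP3A4 inhibitors at screening are all excluded (Section 5.3, criteria 7 to 10). That leaves mainly stand-alone ritonavir newly started on study. Patients are told not to add medication without consulting the investigator, and more frequent hematology monitoring is recommended when a strong inhibitor is started. The appended product characteristics name ritonavir among strong inhibitors and not among their inducer examples. All of this stands and keeps the point small. It does not remove the conflict: the protocol does not say that Appendix 6 overrides Table 14-1, and the label's lists are given as non-exhaustive examples.

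Several stronger readings are tempting, and the documents do not support them.

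- A reader might call the instructions opposite. They are a reduction and no adjustment; neither calls for an increase.
- A reader might think Section 6.4.2 contradicts itself on grapefruit juice. It has no moderate-inhibitor rule, and its reduction is tied to an inhibitor needed for patient management, which fits a food poorly. The fault is an unclear class.
- A reader might extend the ritonavir conflict to combinations such as danoprevir/ritonavir. That combination is listed once, as a strong inhibitor.
- A reader might take exposure figures from the label: an AUC 91% higher gives 1.91 times the exposure with no reduction, and 0.5 x 1.27 = 0.635 times if a moderate inhibitor is handled as strong. Those AUC changes were measured with ketoconazole and erythromycin. No figure is given for ritonavir or grapefruit juice, and the second calculation cannot apply to ritonavir, whose other listing is as an inducer.
- A reader might infer that Section 7.1.4 makes every Appendix 5 drug a ground for stopping, and so creates Week 24 non-responders. The trigger is prohibited treatment, which a permitted drug is not, and the list is permissive.

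**Conclusion.** The point holds as an internal inconsistency in an operative table. Stand-alone ritonavir falls under two conflicting Section 6.4.2 rules with no order of precedence. Grapefruit juice has two mutually exclusive classes and a footnote that does not explain them. The Section 7.1.4 pointer is incomplete.

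Its reach is small. The number of patients is not in the documents; that it will be low is a judgment from the entry criteria. The twofold dose difference is supported for stand-alone ritonavir only, and assumes that two sites each follow a different one of the two instructions. Sample size, power, the primary analysis method and the per-protocol criteria are unaffected. It deserves correction because the repair is cheap. It is not a threat to the trial's conclusions, and no view is taken here on which class or dose is right.

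**What to change.** In the next protocol amendment:

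1. Reconcile Table 14-1 with Section 6.4.2 and the appended product characteristics (Appendix 6, label section 4.5) so that ritonavir and grapefruit juice each lead to one instruction. If a double listing is intended, state which rule prevails. Class and dose are for the sponsor's clinical team.
2. Correct footnote 1 so that it fits the entry it marks.
3. Have the Section 7.1.4 bullet refer to Section 6.4.3 and to the prohibitions in Section 6.4.2, keeping Appendix 5 for the inducers and herbal products those sections prohibit. Pointing to Section 6.4.3 alone would lose the herbal prohibition, which is in Section 6.4.2.

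The cost is an edit to one appendix table, one footnote and one cross-reference, with a matching check of Section 6.4.2. No change to the SAP is needed.
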